8.2.7. Inclusion Criteria

All patients initiating filgotinib in the observational period to treat moderate to severe RA and who comply with the register's requirements for inclusion (including patient consent) will be included. Thus, there is no limit in terms of age, although only adults (≥ 18) are included in ARTIS, or in terms of prior use of filgotinib; initiation is therefore defined as either no prior use or prior use that was discontinued (thus, patients who are non-naïve to filgotinib can be included).

1. Initiation of filgotinib treatment in the observational periods as captured in ARTIS.

2. RA diagnosis by a consulting rheumatologist.

8.2.8. Exclusion Criteria

No exclusion criteria are considered.

8.3. Variables

8.3.1. Baseline Variables

Baseline variables are collected at index date. These variables reflect the patient's demographics and status at the initiation of filgotinib treatment including relevant medical history at or prior to the index date. Age (or date of birth), sex, disease duration and DAS28 are recorded at baseline for all registries.

Risk factors for MACE, VTE, and Serious and Opportunistic Infections

Variables will be collected at baseline to define the risk of each of the 3 outcomes of concern: MACE, VTE, and serious and opportunistic infections (see definitions in Section 6.1 and Annex 4).

The set of risk factor definitions were derived utilizing broader representation than that solely included in the RMP and then checked against data availability in each registry. The set of risk factors are provided in tables in each of the registry-specific sections, which reflect the availability of variables for each registry.

For MACE, the UK's Q-Risk score was used as a guide (Hippisley-Cox et al., 2008). We note that RA is a risk factor for MACE/CVD implying that the indicated patient population are at higher risk than the general population (after adjusting for age and sex). RA is available in all registries as a risk factor, as all patients have RA.

For VTE, the Jyseleca RMP mentions the following risk factors for VTE: "*prior history of VTE, advanced age, hormone replacement treatment, obesity, smoking, cancer or immobilization*". These risk factors are supplemented by considering the Caprini Score (Bahl et al., 2010), a perioperative assessment tool for new VTE. The Caprini Score highlighted the importance of a lack of mobility and hospitalization have on VTE risk.

For serious and opportunistic infections, the RMP highlighted that patients with RA were at increased risk and that the "*The reasons are multifactorial, including a poorly functioning immune system and concomitant use of immunosuppressant medications such as glucocorticoids*". The use of immunomodulators implies that patients initiating filgotinib are already at increased levels of risk. The set of risk factors for infection were supplemented by those indicated by the Rheumatoid Arthritis Observation of Biologic Therapy (RABBIT) Risk Score for serious infections (Zink et al., 2014).

The availability of the variables in each registry that define the risk of MACE, VTE and serious and opportunistic infections is defined in the following sections. Other baseline variables (patient characteristics) captured at baseline are also provided in these sections.

8.3.1.1. ARTIS

Patient Baseline Characteristics

Baseline variables will include the following:

- Age (at baseline)
- Sex
- Renal impairment
 - Stage (if available)
- Date of initiation of filgotinib
- Initial dose of filgotinib
- First ever administration of filgotinib: y/n
- Previous RA treatment immediately prior to initiation of filgotinib
- Date of diagnosis of RA (year; approximate if greater than 10 years earlier)
- Current severity of RA
 - Disease Activity Score (DAS):
 - DAS for 28 joint count (DAS28)
 - DAS28 type: Erythrocyte Sedimentation Rate (ESR); C-reactive protein (CRP)
 - CRP value
 - ESR value
 - Health Assessment Questionnaire (HAQ) score
 - Visual analogue scale (VAS; patient assessment of disease)
 - RA type (seropositive, seronegative)
 - Date of assessment

Risk Factors for MACE, VTE, and Serious and Opportunistic Infections

As previously described, each registry was assessed for the availability of the set of potential risk factors for the 3 endpoints of concern. In ARTIS there are no measures of obesity or immobility, both risk factors for VTE, although HAQ could be used as a proxy.

Table 3 Risk Factors for MACE, VTE and Serious and Opportunistic Infections as Available in ARTIS

	MACE	VTE	Serious and Opportunistic Infections
History of cardiovascular disease	Yes		
History of VTE		Yes	
Previous serious infection			Yes
Age	Yes	Yes	Yes
Sex	Yes		
Diabetes type 1	Yes		Yes
Diabetes type 2	Yes		Yes
Atrial fibrillation	Yes		
Chronic kidney disease	Yes		Yes
Smoking	Yes	Yes	
Family history CVD	Yes		
Use of treatment: Hyperlipidemia (Dx unavailable)	Yes		
Use of treatment: Hypertension (Dx unavailable)	Yes		
Cancer diagnosis (date)	Yes	Yes	Yes
Known thrombophilic condition		Yes	
Reduced mobility / Hospitalization (date, type, length of stay)		Yes	
Trauma and/or surgery		Yes	

	MACE	VTE	Serious and Opportunistic Infections
Ongoing hormonal replacement therapy		Yes	
Heart and/or respiratory failure		Yes	
Acute myocardial infarction or ischemic strokes		Yes	
Chronic lung disease			Yes
Glucocorticoid			Yes
TNFi			Yes
Other immunosuppressant/modifying treatment			Yes

CVD = cardiovascular disease; Dx = diagnosis; MACE = major adverse cardiovascular event; TNFi = tumor necrosis factor inhibitor; VTE = venous thromboembolism

Physician Adherence

In accordance with the RMP, SmPC and the description provided in Section 6.2, the following variables will be used to describe the adherence of the prescribing physician with respect to the Guide for HCP:

- Diagnosis of TB: yes/no
 - Date of diagnosis
- Diagnosis of herpes zoster: yes/no
 - Date of diagnosis
- Diagnosis of viral hepatitis: yes/no
 - Date of diagnosis
- Patient is currently pregnant (defined as greater than 25 weeks): yes/no
- Date of most recent full term pregnancy (for women aged <50 years old)
- Recent diagnosis of serious and opportunistic infection: yes/no
 - Type of infection
 - Date of diagnosis

Dose and age are already variables for this study and thus the use of 100 mg in patients aged ≥ 75 years old and in patients with chronic kidney disease can be addressed.

Concomitant Medication

The SmPC includes a warning that certain concomitant treatments should be avoided. Specifically, combination of filgotinib with other potent immunosuppressants such as azathioprine, ciclosporin, tacrolimus, biologic DMARDs, or other JAK inhibitors is not

recommended as a risk of additive immunosuppression cannot be excluded. For this reason, concomitant use will be recorded; this will not include any previous medication that is discontinued once filgotinib is first prescribed. Thus, this will capture those immunosuppressants that are prescribed to start with filgotinib or that are ongoing.

- Concomitant use of other immunosuppressant:
 - Type, name, and dose (incomplete)
 - Dates of dispensing

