The risk management plan (RMP) classifies MACE and VTE as “*important potential risks*,” while serious and opportunistic infections (and herpes zoster) are considered “*important identified risks*.” TB and other opportunistic infections are more frequent in patients with RA; the reasons are likely multifactorial although increased risk has been identified with the use of glucocorticoids and other biologic DMARDs. To date there have been no safety signals arising from the filgotinib clinical development program for MACE, however the potential role of hyperlipidemia on the risk of MACE warrants continued assessment. Regarding VTEs, there was no imbalance in the occurrence of these events from the clinical development program however the RMP states “*With RA patients and patients with ulcerative colitis having a higher risk of VTEs, and VTEs having been associated with some JAK inhibitors, venous thromboembolism (DVT/PE) has been classified as an important potential risk*”.

Pregnancy is a contraindication for filgotinib as teratogenicity was observed in animals. Thus, women of childbearing potential must be encouraged to use effective contraception during treatment and for at least 1 week after stopping filgotinib treatment.

Serious and opportunistic infections (including herpes zoster and TB) are higher in patients with RA and is increased with the use of prednisone and some biological DMARDs. Thus, there may be increased risk of such infections among patients with poor immune systems or due to the use of immunosuppressant medication.

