6.2. Physician Adherence

Physician adherence implies compliance with the SmPC and the HCP Guide. Firstly, this includes the avoidance of administering filgotinib to contraindicated patients: those with active TB, or active serious infection or being pregnant at initiation of treatment and while continuing filgotinib treatment. Secondly, the physician should undertake appropriate screening prior to prescribing filgotinib: screening for TB and viral hepatitis. Furthermore, information on the use of live, attenuated vaccines during, or immediately prior to, filgotinib treatment, and the provision of guidance to women of childbearing potential will be evaluated. Lastly, prescribed doses should be in line with the recommendations. Thus, this will be evaluated for patients aged

≥ 75 or patients with moderate to severe renal impairment whose starting dose should be 100 mg daily.

In terms of adherence during filgotinib use, several endpoints should be monitored:

- Given that pregnancy is a contraindication for filgotinib, should a woman become pregnant, filgotinib must be discontinued.
- If a VTE occurs (“clinical features of DVT/PE”), filgotinib should be discontinued and the patients be evaluated.
- Patients should be monitored for the development of signs and symptoms of TB.
- Lipid parameters should be monitored at 12 weeks after initiation of treatment.
- Live attenuated vaccines should be avoided during filgotinib treatment.

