7. RESEARCH QUESTION AND OBJECTIVES

The objectives of this study are as follows:

- To quantify the proportion of users of filgotinib being at high risk (as defined in the RMP) of developing MACE, VTE, or serious and opportunistic infections at baseline
- To quantify the proportion of filgotinib users among the very elderly (≥ 75 years) patients being initiated on filgotinib at the recommended dose of 100 mg once daily
- To quantify the proportion of filgotinib users with moderate to severe renal impairment being initiated on filgotinib at the recommended dose of 100 mg once daily
- To quantify the proportion of users of filgotinib who are being treated for active TB at the time of filgotinib treatment initiation and during follow-up (while continuing filgotinib treatment)
- To quantify the proportion of users of filgotinib who have a history of viral hepatitis at the time of filgotinib treatment initiation and during follow-up (while continuing filgotinib treatment)
- To quantify the proportion of female patients of childbearing potential who are pregnant at the time of filgotinib treatment initiation or become pregnant while continuing filgotinib treatment during follow-up
- To assess the proportion of filgotinib users receiving live, attenuated vaccines at the time of filgotinib initiation or at any time during follow-up while continuing filgotinib treatment
- To assess the proportion of filgotinib users with filgotinib discontinuation following a VTE event
- To describe prescribing physicians' adherence to recommendations for patient screening and laboratory monitoring (if available), specifically:
 - To assess the proportion of filgotinib users with evidence of having performed screening for TB prior to initiation of filgotinib
 - To assess the proportion of filgotinib users with evidence of having performed lipid monitoring 12 weeks after initiation of filgotinib
- To assess the proportion of filgotinib users with evidence of having performed the following laboratory tests prior to initiation of filgotinib: absolute neutrophil count (ANC), absolute lymphocyte count (ALC), hemoglobin (Hb) level

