8.2.6. Index Date, Follow-up, Inclusion and Exclusion Criteria

For all analyses, the index date in each registry will be the date a patient starts filgotinib treatment (i.e. the date of first identification of filgotinib exposure in the registry) on or after launch/commercial availability for the treatment of moderate to severe RA and implementation of the aRMMs in each country. The patient follow-up time is defined as the time from the filgotinib index date until the earliest of treatment discontinuation, study withdrawal (withdrawn from the registry, death or loss to follow-up) or end of study.

The observational (study) period for each registry starts at the index date of the first patient starting filgotinib treatment in the registry (i.e. start of data collection). End of the study period will be at 48 months after the start of data collection in the registry (i.e. end of data collection).

To be included a patient has to be aged 18 years or older at the index date. Further inclusion criteria are specified in the following sections for each registry; patients must meet all eligibility criteria.

There are no restrictions to patient inclusion in terms of either historical data or minimum amount of follow-up. Furthermore, patients can be included if they have previously used filgotinib, in which case the patient will have 2 or more treatment lines and therefore 2 or more index dates.

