The Swedish Patient Register collects information on all hospitalized (inpatient-treated) patients, and all visits to nonprimary outpatient care (such as a visit to a rheumatologist). Diagnoses are assigned by the treating/discharging physician, as well as date of discharge, discharging hospital, and department. Diagnoses are coded according to the International Statistical Classification of Diseases and Related Health Problems (ICD), with Version 8 used until 1986, Version 9 from 1987 to 1996, and Version 10 since 1997. The inpatient component was originally initiated by several counties in 1964, had 85% countrywide coverage in 1983, and is considered complete since 1987. Validation against medical files have found an overall error rate in the main diagnoses of 4% at the ICD chapter level, and 12% at the 3-digit level. The outpatient component of the Swedish Patient Register was initiated with nationwide coverage in 2001. Overall, 13% of outpatient visits lack records, but coverage is higher for somatic public care (including most rheumatology care). Chart reviews and validation of the RA diagnosis based on different algorithms applied to the register data indicate a positive predictive value for a register-based diagnosis of RA around 90% (S. Eriksson et al., 2013; Knight et al., 2008).

C) The Swedish Cancer Register

The Swedish Cancer Register was established in 1958 and contains information on date of cancer (and some selected precancers) onset, and type of cancer according to the ICD classification and morphology/histology. Approximately 99% of cancers have been morphologically verified. Reporting of incident cancers (including invasive malignancies as well as cancer in situ) is mandatory and semiautomated, resulting in an estimated coverage greater than 95% (Barlow et al., 2009; Mattsson & Wallgren, 1984).

D) The Medical Birth Register

The Medical Birth Register contains prospectively provided data from antenatal, obstetric, and neonatal records since 1973, and covers all live and still births (but not all miscarriages) in Sweden. Among the variables covered are maternal age, parity, smoking and family situation in early pregnancy, and the infant's birth weight and length, gestational age (primarily based on ultrasound dating), and Apgar score. Complications and mother's and infant's morbidities are coded according to the ICD, with Version 8 used until 1986, Version 9 from 1987 to 1996, and Version 10 since 1997.

E) The Cause of Death Register

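### ARTIS codes a woman as pregnant at filgotinib start only beyond 25 weeks, so as written earlier pregnancies at initiation are recorded as not pregnant

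*Protocol*

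**What the plan says.** Section 7 of the protocol sets the objective: "To quantify the proportion of female patients of childbearing potential who are pregnant at the time of filgotinib treatment initiation or become pregnant" while on treatment. Section 6.1 gives the reason: "Pregnancy is a contraindication for filgotinib as teratogenicity was observed in animals". Section 6.2 adds, for the treatment period, "should a woman become pregnant, filgotinib must be discontinued". None of these carries a gestational limit.

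Section 8.3.1.1 lists the ARTIS variables that will describe prescriber adherence at baseline. Pregnancy appears there as "Patient is currently pregnant (defined as greater than 25 weeks): yes/no". The only other ARTIS pregnancy item is "Date of most recent full term pregnancy (for women aged <50 years old"). ARTIS has no item for weeks of gestation.

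For follow-up, Table 9 (section 8.3.2) marks pregnancy as available in ARTIS without a definition. Section 8.7 reports the women aged 18 to 49 who become pregnant, again with no gestational limit. Section 8.4.1 describes the linked Medical Birth Register, which holds gestational age and "covers all live and still births (but not all miscarriages) in Sweden".

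**The concern.** The variable does not measure what the objective asks for. Pregnancy at initiation is a contraindication, and its frequency is one of the results by which the risk minimization measures will be judged. Under the ARTIS definition, a woman who starts filgotinib at week 8, 16 or 24 counts as adherent prescribing. The error runs in one direction only: a low ARTIS figure could reflect good adherence or simple non-detection, and the report could not tell them apart. The consolidated reports will also show ARTIS beside four registries that record pregnancy without this threshold.

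**Working it through.** This is mainly a comparison of definitions. The arithmetic afterwards is illustrative.

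**Definitions side by side (section 8.3.1)**

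| Registry | Pregnancy at baseline | Weeks recorded | Threshold |
|---|---|---|---|
| ARTIS (8.3.1.1) | yes/no | no | more than 25 weeks |
| BIOBADASER (8.3.1.2) | yes/no | yes | none |
| BSRBR-RA (8.3.1.3) | yes/no | no | none |
| DANBIO (8.3.1.4) | yes/no | yes | none |
| RABBIT (8.3.1.5) | yes/no | yes | none |

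**Does anything else in ARTIS recover the early starts?** The full-term item is a baseline date. It does not cover preterm births or losses, and no rule turns it into pregnancy status on the index date. The Medical Birth Register could date a pregnancy back to the index date, but the protocol does not say it will be used that way. The limitations in section 8.9 do not mention the threshold.

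**Two readings**

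1. Gestation on the index date must exceed 25 weeks. Every start at or before week 25 is coded no.
2. Only pregnancies that last beyond 25 weeks are identifiable. A woman who starts at week 5 and later delivers could be counted, but a pregnancy that ends by week 25 is missed. Embryolethality is among the topics of the healthcare professional guide (section 6.1).

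Both readings remove cases from the numerator and leave the denominator unchanged, so the proportion can only fall.

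**The plan's own benchmark.** Table 10 (section 8.5) uses the rule of 3, n = 3/p. For p = 1%, 3/0.01 = 300, as stated. The exact chance of at least one case is 1 − (1 − 0.01)^300 = 95.1%. The other four rows also reproduce (150, 100, 75 and 60; exact certainty 95.2% to 95.4%).

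**Illustration under reading 1.** Assumptions, none of them from the protocol: a 40-week pregnancy, a true pregnancy proportion of 1%, and 300 women in the group assessed. If a share s of pregnant starts falls after week 25, the apparent proportion is 0.01 × s, the chance of at least one recorded case is 1 − (1 − 0.01s)^300, and the rule-of-3 size is 3/(0.01s).

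| Timing of starts | s | Missed | Chance of at least one in 300 | Rule-of-3 n |
|---|---|---|---|---|
| No threshold | 1 | 0% | 95.1% | 300 |
| Three quarters after week 25 | 0.75 | 25% | 89.6% | 400 |
| Even over 40 weeks | 15/40 = 0.375 | 25/40 = 62.5% | 67.6% | 800 |
| Even over the first 30 weeks | 5/30 = 0.167 | 83.3% | 39.4% | 1,800 |
| All at or before week 25 | 0 | 100% | 0% | none suffices |

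Table 10 concerns any contraindication among all users, whereas pregnancy is assessed only in women of childbearing potential. The table above therefore shows the mechanism and does not forecast ARTIS results.

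**The case against.** The strongest reply is that the wording describes availability. Section 8.3.1 says the registry sections reflect what each registry holds, ARTIS draws on a birth register, and 25 weeks may mark which pregnancies that register can identify. This is plausible, and it would rescue women who start early and later deliver. It does not rescue pregnancies that end earlier. The text also says defined as, and the protocol gives neither a back-dating rule nor a stated limitation, although it flags other gaps openly, such as the Table 9 notes on hepatitis history and zoster-only vaccine data.

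A reader might infer that pregnancies arising on treatment are lost too: the drug must be stopped, and follow-up runs "until the earliest of treatment discontinuation, study withdrawal" or end of study, so a woman who stops by week 25 would never qualify. The documents do not support this as a finding. The threshold stands only among the baseline variables; Table 9 and section 8.7 give none. Ending follow-up at discontinuation also does not bar the use of later linked records to date a pregnancy that began on treatment. The loss would arise only if the threshold were carried over and read literally.

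A reader might also infer that the missed pregnancies are the ones of greatest concern. The protocol does not rank gestational periods.

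On comparability, it is fair to say that each registry analyses its own data, that no pooled pregnancy estimate is specified, and that BSRBR-RA does not record weeks either. What stands is that ARTIS alone has a threshold, and that its result will appear in the same consolidated report.

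**Conclusion.** The baseline definition is wrong as written. It contradicts the objective and the contraindication, is unique to ARTIS, and is neither justified nor disclosed. Following it biases the ARTIS proportion of women pregnant at initiation downwards on either reading. The amount cannot be derived from the protocol, which gives neither gestational age at start nor an expected number of pregnancies. The 62.5% and 100% figures are conditional on assumed timing of starts under the literal reading; losses under the second reading are not quantified. For pregnancy during follow-up the protocol is silent on the threshold, so any loss there is conditional. The conclusion rests on the definition itself and not on the illustrative percentages.

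**What to change.** 1. Delete the 25-week threshold in section 8.3.1.1.
2. Define ARTIS pregnancy, at initiation and during treatment, as overlap between filgotinib exposure and the pregnancy interval. The interval starts at delivery date minus gestational age, both taken from the Medical Birth Register, and ends at the end of pregnancy. Use linked records dated after discontinuation where available.
3. Add pregnancy-loss diagnoses from the Patient Register where available.
4. Reconcile section 8.3.1.1 with sections 6.2, 7 and 8.3.2, and state in Table 9 what the ARTIS entry covers.
5. State in section 8.9 the under-ascertainment that remains: early losses, which neither register records completely, and pregnancies not yet delivered at the data cut.

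The cost is some programming on a linkage that section 8.4.1 already describes, plus protocol wording. Pregnancies conceived late may be incompletely captured at the cut, and the 1 to 2 year linkage lag stated in section 8.4.1 adds to this. A mandatory look-forward period with a separate reporting cut is not needed to repair the defect; disclosing the limit is enough.

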- Diagnosis of viral hepatitis: yes/no
 - Date of diagnosis
- Patient is currently pregnant: yes/no
 - Weeks pregnant
- Date of most recent full term pregnancy (for women aged < 50 years old)
- The patient is suffering from a serious and opportunistic infection (as defined by MedDRA): yes/no
 - Infection type
 - Date of diagnosis

Dose and age are already variables for this study and thus the use of 100 mg in patients aged ≥ 75 years old and in patients with chronic kidney disease can be addressed.

- Screening:
 - TB
 - Date of screening
 - Result of screening test

Concomitant Medication

- Concomitant use of other immunosuppressant:
 - Type, name, and dose (where recorded)

Additional Variables: Laboratory and Counselling

BIOBADASER is the only registry that can supplement their data through additional data collection screens based on clinical practice. The additional variables are summarized below.

Table 5 Additional Variables in BIOBADASER

Variable			
ANC (neutrophils)	Value	units	Date
ALC (lymphocytes)	Value	units	Date
Hb	Value	units	Date
HDL	Value	units	Date
LDL	Value	units	Date
Total cholesterol	Value	units	Date
triglycerides	Value	units	Date
HDL:LDL	Value	units	Date
Advice given on contraceptive use	y/n		
Advice given on spermatogenesis	y/n		
Advice given on breast feeding	y/n		

ALC = absolute lymphocyte count; ANC = absolute neutrophil count; Hb = hemoglobin; HDL = high density lipoprotein; LDL = low density lipoprotein

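### Read literally, the ARTIS definition of current pregnancy counts only women beyond 25 weeks, so the proportion pregnant at filgotinib start is understated and not comparable with the other four registries

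*Protocol*

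**What the plan says.** Section 7 sets the objective: "To quantify the proportion of female patients of childbearing potential who are pregnant at the time of filgotinib treatment initiation or become pregnant while continuing" the drug. It carries no gestational limit. Section 6.1 gives the reason: "Pregnancy is a contraindication for filgotinib as teratogenicity was observed in animals". Section 6.2 defines adherence as not giving the drug to contraindicated patients, namely "those with active TB, or active serious infection or being pregnant at initiation of treatment and while continuing filgotinib treatment".

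Section 8.3.1.1 (ARTIS, Physician Adherence) says that "the following variables will be used to describe the adherence of the prescribing physician with respect to the Guide for HCP", and the list includes "Patient is currently pregnant (defined as greater than 25 weeks): yes/no". The only other pregnancy item there is the date of the most recent full-term pregnancy in women under 50. Under Section 8.3.1, baseline variables are taken at the index date and include history at or before it.

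BIOBADASER (Section 8.3.1.2) has "Patient is currently pregnant: yes/no" with weeks pregnant as a sub-item. DANBIO (8.3.1.4) and RABBIT (8.3.1.5) have the same pair. BSRBR-RA (8.3.1.3) has a plain yes/no for pregnancy without weeks.

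Section 8.4.1 describes linkage of ARTIS to the Medical Birth Register. That register covers live births and stillbirths but not every miscarriage, and its fields include "gestational age (primarily based on ultrasound dating").

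**The concern.** The variable that serves the initiation part of the objective carries a restriction that the objective does not have. A woman at week 8 or week 20 on her index date is pregnant under Sections 6.1, 6.2 and 7, yet scores no on the ARTIS item as written. That includes women who go on to deliver and whose birth and gestational age the linked register would hold.

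Pregnancy is one of the three contraindications that Section 6.1 takes from the SmPC, the others being active TB and active serious infection. The study exists to show whether prescribers avoid them. An ARTIS figure lowered by its definition would look like better adherence. It would also stand in the consolidated report for the EMA and the MHRA (Section 11.1) beside figures from four registries that measure something wider.

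**Working it through.** The protocol gives no expected pregnancy proportion and no figure for this variable, so there is nothing of its own to reproduce. The check has two parts.

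**1. The definitions side by side**

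| Place in the protocol | Who counts as pregnant at start | Threshold |
|---|---|---|
| Section 7, objective | any woman of childbearing potential pregnant at initiation | none |
| Sections 6.1 and 6.2 | pregnancy as a contraindication | none |
| 8.3.1.1 ARTIS | currently pregnant | more than 25 weeks |
| 8.3.1.2 BIOBADASER | currently pregnant, with weeks | none |
| 8.3.1.3 BSRBR-RA | pregnancy yes/no | none |
| 8.3.1.4 DANBIO | currently pregnant, with weeks | none |
| 8.3.1.5 RABBIT | currently pregnant, with weeks | none |

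ARTIS is the only entry with a limit, and no reason is given for it. The limit turns true yes values into no and never the reverse, so the direction of the error is fixed.

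**2. The share missed, under stated assumptions**

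The protocol does not say how gestational week at start is distributed, so each line rests on an assumption.

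- Starts spread evenly over a gestation of G weeks: share scored no = 25/G.
  - G = 42: 25/42 = 59.5%
  - G = 40: 25/40 = 62.5%
  - G = 37: 25/37 = 67.6%
- All starts in the first w weeks, with w no greater than 25: share scored no = w/w = 100%. This covers w = 6, 8 and 12.

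**3. Whether another ARTIS item recovers these women**

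- The date of the last full-term pregnancy is a baseline item, at or before index. It does not identify a pregnancy in progress.
- Pregnancy is a follow-up variable for ARTIS in Table 9 (Section 8.3.2), without a definition. Section 8.7 reports women aged 18 to 49 who become pregnant after starting. A woman already pregnant at index who stays on treatment might appear there, but as a new pregnancy on treatment rather than one present at initiation.
- Under Section 8.2.6 follow-up ends at discontinuation. A woman who stops once the pregnancy is recognised may be counted in neither place.

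**The case against.** The strongest reply is that the parenthesis was meant differently. ARTIS takes much of its data by register linkage, and the next item on the list concerns full-term pregnancy. The authors may have meant a pregnancy that lasted more than 25 weeks, that is, one that reaches the Medical Birth Register. On that reading a woman who starts at week 8 and later delivers is counted. This is possible, so it cannot be said for certain that such women will be excluded. But the cut-off is attached to being currently pregnant, and a programmer following the line would apply it to gestational week at index. The line has to be rewritten under either reading.

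It is also fair to say that the follow-up variable may pick up some of these women. That stands in part: they would be recovered under the wrong heading, and only if they remain on treatment.

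A third reply is that the study is descriptive, has no hypotheses and takes variables as each registry holds them. That limits the consequence but does not excuse the cut-off. For pregnancies ending in birth, the linked register as described holds gestational age, so availability does not force a 25-week limit.

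Two stronger readings are tempting and are not supported. A reader might infer that ARTIS must report close to 0%. That does not follow: women beyond 25 weeks still count, and under even starts over 40 weeks 37.5% of pregnant starters (15/40) would be captured. A reader might also put the missed share into the illustration in Section 8.5 (1% and 300 patients) and quote a loss in the chance of seeing a case. That 1% is for any contraindication among all users. It is not pregnancy, not restricted to women aged 18 to 49, and not specific to the one registry of five with this rule.

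**Conclusion.** The point holds on the literal text. The ARTIS definition contradicts the objective in Section 7 and the contraindication and adherence statements in Sections 6.1 and 6.2, and it differs from all four other registries. As written, it can only understate the ARTIS proportion pregnant at start, and it makes that proportion non-comparable across registries.

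The size is not known from the protocol. It is about 60% to 68% of pregnant starters missed if starts are even over 37 to 42 weeks, and 100% if all starts fall in the first 12 weeks. Under the alternative reading of the parenthesis, women who later deliver would not be lost, and the fault reduces to wording that invites the wrong rule.

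The effect is confined to the ARTIS pregnancy result and its place beside the others. It does not touch the other objectives. It is still worth correcting before programming: the protocol fixes a definition that works against one of its own objectives, and the correction is small.

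**What to change.** In Section 8.3.1.1, remove the 25-week threshold and define the variable by dates. A woman is pregnant at index if her index date lies between estimated conception and birth, for every live birth and stillbirth in the Medical Birth Register. Estimated conception is back-calculated from birth date and gestational age, and the convention for doing so should be stated. Then:

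- Report gestational week at index for ARTIS, as BIOBADASER, DANBIO and RABBIT can. BSRBR-RA records only yes/no and should be footnoted.
- Count these women as pregnant at initiation, and keep them out of the Section 8.7 count of women who become pregnant during follow-up.
- State that losses not held in the register are not captured, nor are births not yet linked at the time of analysis (Section 8.4.1 gives a lag of 1 to 2 years). Removing the threshold without saying this would present births-only data as all pregnancies.

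The cost is one rewritten line, a short limitation note and a date calculation within a linkage the protocol already describes. Section 8.4.1 names gestational age but does not list birth date among the register's fields, so its availability in the extract should be confirmed. No new data collection is expected.
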